Patients with metastatic disease, those whose tumors don't become amenable to resection, and those with residual disease following an attempted surgical resection will continue larotrectinib for up to 26 cycles (approximately 2 years) on this protocol. Such patients will subsequently complete planned therapy and enter Follow-up. Patients who are continuing to experience benefit from larotrectinib at the completion of 26 cycles of therapy and for whom their treating physician determines it is not in their best interest to discontinue therapy and be observed may be able to continue treatment utilizing commercial supply (if approved by the local health authority), an expanded access protocol, or single patient protocol as appropriate and available at that time.

Patients with localized disease who achieve a complete response to therapy will continue receiving larotrectinib for a minimum of 12 cycles (approximately 1 year) or 6 cycles after achieving the complete response (whichever is later). Subsequently, such patients will be observed on study off of therapy unless they experience recurrence.

Patients with TRK fusion leukemias have not been included on any clinical trials of larotrectinib. However, we hypothesize there will be a high level of activity in such patients based on the responses seen in patients with TRK fusion solid tumors, the partial response reported in an adult with an *NTRK2* fusion AML, and the responses to kinase inhibition seen in children and adults with leukemias harboring *BCR-ABL* fusions. Children with relapsed/refractory leukemias with TRK fusions will be treated with larotrectinib at the established pediatric phase 2 dose of 100 mg/m²/dose BID with a cap of 100 mg/dose. Following 1 cycle (28 days) of this therapy, patients will undergo a disease evaluation to assess response. Patients without progressive disease may continue to receive larotrectinib at their treating physician's discretion for a maximum of 26 cycles.

This is a non-randomized study given the high response rate seen in the relapsed setting and rarity of the patient population. With an expected enrollment of ~6-8 patients with IFS per year, a randomized study with sufficient power to show equivalence or superiority of larotrectinib to standard of care chemotherapy is not feasible within a reasonable accrual timeframe.

The FDA approved larotrectinib during the course of the study, but the study will proceed as written.

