6.2.2 Toxicity: (Intrathecal)

| | Common Happens to 21-100 children out of every 100 | Occasional Happens to 5-20 children out of every 100 | Rare Happens to < 5 children out of every 100 |
|---|--|--|---|
| Immediate: Within 1-2 days of receiving drug | Nausea, vomiting, fever, headache | Arachnoiditis | Rash, somnolence, meningismus, convulsions, paresis |
| Prompt: Within 2-3 weeks, prior to the next course | | | Myelosuppression, ataxia |
| Delayed: Any time later during therapy, excluding the above condition | | | Necrotizing leukoencephalopathy, paraplegia, blindness (in combination with XRT & systemic therapy) |

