9.0 STATISTICAL CONSIDERATIONS

9.1 Sample Size and Study Duration

One disease stratum (infantile fibrosarcoma, Cohort A) has been identified as the primary cohort for reporting upon completion of evaluation. The evaluation rule is described in [Section 9.2](#) below. In addition to the main stratum, enrollment into each of the following tumor

groups (“secondary strata”): (B) Other newly-diagnosed TRK fusion solid tumors, and (C) Relapsed/refractory acute leukemias; will be open to accrual. If nine response-evaluable patients of a particular histology are enrolled in either of the secondary strata, the two-stage design described in [Section 9.2](#) below will be applied to that particular histology. (That is, up to twelve additional response-evaluable patients with that tumor type may be studied.) Upon completion of enrollment to Cohort A, the study committee will make a decision on whether to continue enrollment to the secondary strata or to close the study. This will be based on the enrollment and response rates observed in the strata up until that date.

Review of SEER data indicates the following entry rate can be expected, assuming that 33% of patients with infantile fibrosarcoma have resectable disease at diagnosis, and 33% of the remaining patients don’t enroll on this study for other reasons:

| Disease Group/Strata | Patients/Year |
|-----------------------------|----------------------|
| Infantile fibrosarcoma | 8 |

Assuming an annual enrollment rate of 8 patients/year in Cohort A, the probability of accruing 9 patients to complete the initial stage of evaluation within 17 months is 80% and within 26 months is 90%. The corresponding probability for enrolling 21 patients in 37 months is 80% and within 47 months is 90%. Allowing for a 10% inevaluability rate, a minimum of 9 and a maximum of 70 patients will be enrolled. The study will likely require 3 to 4 years for sufficient patient enrollments to evaluate larotrectinib in IFS.

Assuming all three cohorts fill completely, a maximum of 63 evaluable patients will enroll. Accounting for up to an estimated 10% of patients in Cohort A who do not meet the definition of evaluable for response and therefore require replacement, a maximum of 70 total patients will enroll.

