9.3.1 Adverse Event Monitoring Rule

We will use a Bayesian rule to monitor for protocol-specific toxicities (list given below). We will assume a beta prior distribution with $\alpha = 0.52$ and $\beta = 2.08$. At least once per month, we will calculate the posterior probability (given the data) that the probability of protocol-specific toxicity exceeds the 20% threshold:

$$P(p_{\text{protocol-specified toxicities}} > 20\% \mid \text{Data}) = \int_{0.2}^1 \frac{\binom{n}{x} p^x (1-p)^{n-x} \frac{\Gamma(2.6)}{\Gamma(0.52)\Gamma(2.08)} p^{-0.48} (1-p)^{1.08}}{\int_0^1 \binom{n}{x} q^x (1-q)^{n-x} \frac{\Gamma(2.6)}{\Gamma(0.52)\Gamma(2.08)} q^{-0.48} (1-q)^{1.08} dq} dp$$

Here n is the number of protocol-specific toxicity-evaluable cycles and x is the number of such cycles on which a protocol-specific toxicity event is observed. If there is strong evidence (posterior probability of at least 70% with at least 2 observed toxicities) that there is a per course protocol-specific toxicity probability

of more than 20%, such information will be presented to the DSMC. Examples of situations in which this rule will indicate protocol-specific toxicities have been noted and are presented below:

| Number of failures | Number of patient-cycles |
|--------------------|--------------------------|
| 2 | 6 |
| 3 | 10 |
| 4 | 14 |
| 5 | 19 |
| 6 | 23 |
| 7 | 28 |
| 8 | 32 |
| 9 | 37 |
| 10 | 41 |
| 11 | 46 |
| 12 | 51 |
| 13 | 55 |
| 14 | 60 |

Protocol-specific toxicities of interest include CTCAE v5 Grade 3 or higher fatigue, ataxia, dizziness, ALT increase, AST increase, neutropenia, thrombocytopenia, nausea, and vomiting. For the purpose of this toxicity monitoring rule, patients with leukemia or solid tumors with bone marrow metastases are not evaluable for hematologic toxicities (neutropenia or thrombocytopenia) unless these persist for greater than 14 days after a bone marrow is negative for malignancy and the patient does not have evidence of recurrent disease.

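### The toxicity alert in Section 9.3.1 runs over all cohorts together, so excess toxicity confined to Cohort C is increasingly hidden as solid-tumor cycles accumulate

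*Combined protocol and SAP*

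**What the plan says.** Section 9.3.1 puts a Beta(0.52, 2.08) prior on a single toxicity probability. At least monthly it calculates the posterior probability "that the probability of protocol-specific toxicity exceeds the 20% threshold". An alert needs a "posterior probability of at least 70% with at least 2 observed toxicities", and its only stated consequence is that the information goes to the DSMC.

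The counting unit is the cycle: "Here n is the number of protocol-specific toxicity-evaluable cycles". Neither n nor x carries a cohort index, and there is one table of boundaries. The nine monitored events are Grade 3 or higher fatigue, ataxia, dizziness, ALT increase, AST increase, neutropenia, thrombocytopenia, nausea and vomiting.

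Leukemia patients are inside the same rule with a carve-out: "patients with leukemia or solid tumors with bone marrow metastases are not evaluable for hematologic toxicities (neutropenia or thrombocytopenia", except where these persist for more than 14 days after a negative marrow and without recurrent disease. The section does not say whether such cycles remain in n.

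Section 9.2, by contrast, applies its efficacy design in each stratum. On Cohort C, Section 2.5 says: "Patients with TRK fusion leukemias have not been included on any clinical trials of larotrectinib". Sections 4.4.3 and 4.5.3 give intrathecal chemotherapy to Cohort C only, around and during Cycle 1 and with each later cycle.

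**The concern.** Pooling is reasonable when the groups share roughly one toxicity rate. Here the protocol itself separates them: a different disease, a different regimen, no earlier larotrectinib trial experience, and a different effective event list (two of the nine events generally cannot count for leukemia).

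Cohort C is also likely to be small. Section 2.1.5 calls TRK fusions rare in Ph-like ALL and cites four children identified in one sequencing effort. Solid-tumor patients may receive up to 26 cycles (Section 4.1.3), so they will supply most of n. If Cohort C had excess toxicity, the only quantitative trigger in the plan would be the one least able to show it. Aim 1.2.3 covers toxicity in both solid tumors and acute leukemia, yet the toxicity tables in Section 9.3 are specified by type and grade, not by cohort.

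**Working it through.** **Inputs from the plan.** Prior Beta(0.52, 2.08), threshold 20%, posterior cut-off 70%, at least 2 events (Section 9.3.1). The Simon design in Section 9.2 takes 9 + 12 = 21 evaluable patients per stratum. Section 9.1 gives the ceiling: "Assuming all three cohorts fill completely, a maximum of 63 evaluable patients will enroll". That is 3 × 21, so at most 42 in Cohorts A and B.

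**Assumptions, not in the plan.** The true per-cycle rates and the number of cycles per cohort. Cohort C is taken at 6 to 20 cycles. Cycles arrive in random order and the rule is checked after each one.

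**Formula.** P(p > 0.20 | x, n) is the upper tail beyond 0.20 of a Beta(0.52 + x, 2.08 + n − x) distribution.

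**Reproducing the plan's table.** For each x, take the largest n with posterior at least 0.70. All 13 rows match. For example, 2/6 gives 0.7001 and 2/7 gives 0.632; 14/60 gives 0.7135 and 14/61 gives 0.691.

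**Fixed examples of masking.**
- Cohort C at 3/6 is Beta(3.52, 5.08), posterior 0.906: an alert. Add five clean solid-tumor cycles and 3/11 is Beta(3.52, 10.08), posterior 0.660: no alert.
- Cohort C at 10/20 is Beta(10.52, 12.08), posterior 0.997. Pool it with 84 solid-tumor cycles (42 × 2) carrying 4 events: 14/104 is Beta(14.52, 92.08), posterior 0.037. At n = 104 the pooled rule needs 24 events, so all 20 Cohort C cycles would have to be toxic (24/104 gives 0.764).
- With 252 solid-tumor cycles (42 × 6) and 13 events, even 20/20 in Cohort C gives 33/272, posterior 0.0003.

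**Chance of ever alerting** (simulation; Cohorts A and B at 5%, Cohort C at 40%, 120 solid-tumor cycles):

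| Cohort C cycles | Pooled rule | Same rule, Cohort C alone |
|---|---|---|
| 6 | 7% | 77% |
| 12 | 10% | 89% |
| 20 | 16% | 96% |

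About 4 points of each pooled figure is background: the pooled rule alerts in about 4% of trials when Cohort C is also at 5%.

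**Sensitivity to the solid-tumor count** (Cohort C at 40% with 6 to 20 cycles, solid tumors at 2% to 5%): the pooled rule alerts in 5% to 31% with 60 solid-tumor cycles and 1% to 8% with 240. With 42 solid-tumor cycles at 5% and 21 Cohort C cycles it reaches about 46%, against 96% for Cohort C alone. The loss therefore grows with solid-tumor cycles.

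**The other direction** (Cohorts A and B at 25%, Cohort C at 5%, 120 solid-tumor cycles): solid tumors alone alert in about 94%. Pooled, this becomes about 92%, 89% and 85% with 6, 12 and 20 leukemia cycles, and about 64% with 60.

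**False alerts with two streams** (120 solid-tumor cycles). At a true 10% everywhere, the pooled rule and the A and B stream each alert in about 16%, and the Cohort C stream in about 11%, 13% and 15% with 6, 12 and 20 cycles. At least one alert:
- 6 cycles: 1 − 0.84 × 0.89 = 25%
- 12 cycles: 1 − 0.84 × 0.87 = 27%
- 20 cycles: 1 − 0.84 × 0.85 = 29%, or 28% with unrounded inputs

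At a true 5% the rise is from about 4% to 7%. At a true 20%, the threshold itself, the Cohort C stream alone alerts in about 34% to 52%.

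**The case against.** Several points on the other side stand.

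- **Timing.** Section 2.7.1 says accrual is complete, so the change cannot protect future enrollees. The documents give neither the number enrolled in Cohort C nor whether anyone remains on therapy.
- **Other safeguards.** Section 12.2 has the DSMC review interim toxicity and requires unexpected frequencies of serious events to be brought to it. Section 11.8 requires 24-hour notification of SAEs. Section 5.1.2 has a leukemia-specific DLT, although it governs individual dose modification. With few patients, case-by-case review does much of the work. None of these is a quantitative trigger for the cohort, but Cohort C is not unmonitored.
- **Wording.** The section never says that the rule is pooled. That is read from the single p, n and x and from the leukemia clause within the rule.

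Three stronger readings are tempting and are not supported.

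- A reader might infer that the two groups mask each other equally. They do not: hiding of solid-tumor signals is minor unless Cohort C contributes many cycles. At a true 30% in Cohorts A and B, with 120 solid-tumor and 6 leukemia cycles, the pooled rule still alerts in about 99%.
- A reader might infer that expected vomiting after intrathecal drugs would set off alerts. Section 6.2.2 does list "Nausea, vomiting, fever, headache" as common, and Section 6.3.2 is similar, but neither gives a grade and the rule counts only Grade 3 or higher. Section 6.4.2 lists vomiting as rare for single-agent methotrexate, apart from its place within occasional arachnoiditis.
- A reader might take it that leukemia cycles stay in n while their hematologic events are dropped. The text leaves this open.

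**Conclusion.** The point holds in one direction. As written, Section 9.3.1 has little ability to flag excess toxicity confined to Cohort C once solid-tumor cycles dominate: about 7% to 16% pooled against 77% to 96% for Cohort C alone, over 6 to 20 Cohort C cycles. Those figures rest on assumed rates (5% and 40%), 120 solid-tumor cycles and a check after every cycle. The gap is narrower with fewer solid-tumor cycles and wider with more. The fixed posterior examples need no assumed rates, only illustrative counts.

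This is a worthwhile, inexpensive improvement to a review-only alert, not a failure of safety oversight. With accrual complete, its practical reach is any patient still on therapy and the review of toxicity by cohort.

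**What to change.** In Section 9.3.1, state that the existing prior, 20% threshold, 70% cut-off, two-event minimum and boundary table apply separately to (i) Cohorts A and B combined and (ii) Cohort C, and that an alert in either goes to the DSMC. State also whether cycles not evaluable for neutropenia and thrombocytopenia count in n. No boundary, dose or treatment rule changes.

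The cost is two sentences, one more calculation at each review, and the additional false alerts set out above. The section should state those rates so that the DSMC reads a Cohort C alert as a prompt for review rather than as proof of excess toxicity.

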9.4 Evaluability for Response

Any patient who is enrolled and receives at least one dose of larotrectinib will be considered evaluable for response provided: (1) the patient demonstrates progressive disease or death while on protocol therapy; or (2) the patient is observed on protocol therapy for at least one cycle and the tumor is not removed surgically prior to the time complete response or partial response is confirmed, or (3) the patient demonstrates a complete or partial response as confirmed according to protocol criteria. Patients who demonstrate a complete or partial response confirmed by central review will be considered to have experienced a response for the application of the rule given in [Section 9.2](#). All other patients will be considered non-responders. The evaluation period for determination of the best response will be 6 treatment cycles. All patients considered to have a response (CR or PR) must have imaging studies reviewed centrally at the COG. Centers will be notified by the COG about requests for scans of patients with stable disease. See [Section 7.4](#) regarding shipping instructions. Preliminary assessment of activity using institutionally provided tumor measurements will be entered into CDUS quarterly. The central review by COG will be provided as the final reviewed assessment of response when such becomes available.

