8.0 CRITERIA FOR REMOVAL FROM PROTOCOL THERAPY AND OFF STUDY CRITERIA

8.1 Criteria for Removal from Protocol Therapy

- a) Clinical (including physical examination or serum tumor markers) or radiographic evidence of progressive disease or treatment failure while on study (See [Section 10.3.3](#), [Section 10.5.2](#), [Section 10.5.3](#), [Section 10.6.6](#), and [Section 10.7.5](#)).
- b) Adverse Events requiring removal from protocol therapy, as stated in [Section 5.0](#).
- c) Patients who receive concurrent investigational therapy or anticancer therapy, as stated in [Section 3.3.2.3](#) and [Section 3.3.2.4](#).
- d) Refusal of further protocol therapy by patient/parent/guardian.
- e) Physician determines it is in patient's best interest.
- f) Repeat eligibility studies (if required) are outside the parameters required for eligibility prior to the start of larotrectinib ([Section 3.2.6](#)).
- g) Non-compliance that in the opinion of the investigator does not allow for ongoing participation.
- h) Patients who develop a second malignant neoplasm.
- i) Study is terminated by sponsor.
- j) Pregnancy
- k) Completion of planned therapy per [Section 4.1](#).
- l) Patients with leukemia who have persistent CNS disease that does not clear by the end of Cycle 1.

Patients who are removed from protocol therapy are to be followed until they meet the criteria for Off Study ([Section 8.2](#)). Follow-up data will be required unless consent was withdrawn.

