9.3 Methods of Analysis

Response criteria are described in [Section 10.2](#). A responder is defined as a patient who achieves a best response (as defined in [Section 10.3.4](#)) of PR or CR on the study. Response rates will be calculated as the percent of evaluable patients who are responders, and confidence intervals will be constructed accounting for the two-stage design.

Toxicity tables will be constructed to summarize the observed incidence by type of toxicity and grade. A patient will be counted only once for a given toxicity for the worst grade of that toxicity reported for that patient. Toxicity information recorded will include the type, severity, time of onset, time of resolution, and the attribution(s) to the study regimen.

Time-to-event analyses (time to progression, progression-free survival, overall survival, and duration of response) will be computed one year after the last enrollment in a stratum. Duration of response will be defined among patients with a confirmed best response of either PR and CR, and will be defined as the time from the first observation of either PR or CR until either the first observation of PD (event) or last known observation of the patient (censored observation).

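### Treated patients who leave therapy in Cycle 1 without a confirmed response can drop out of the primary response rate and be replaced, so the evaluable rate is at or above the all-treated rate

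*Combined protocol and SAP*

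**What the plan says.** Section 9.4 applies to enrolled patients who receive at least one dose of larotrectinib. Such a patient is evaluable for response by any one of three routes:

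- Route 1: "the patient demonstrates progressive disease or death while on protocol therapy".
- Route 2: "the patient is observed on protocol therapy for at least one cycle", provided the tumor was not resected before a response was confirmed.
- Route 3: "the patient demonstrates a complete or partial response as confirmed according to protocol criteria". This route carries no minimum exposure and no requirement to be on therapy.

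After stating that centrally confirmed responses count for the two-stage rule, the section adds: "All other patients will be considered non-responders". The window is also fixed there: "The evaluation period for determination of the best response will be 6 treatment cycles".

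Two other sections determine what evaluability does. Section 9.3 sets the denominator: "Response rates will be calculated as the percent of evaluable patients who are responders". Section 9.1 allows for up to 10% of Cohort A patients "who do not meet the definition of evaluable for response and therefore require replacement".

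Section 8.1 lists reasons for leaving protocol therapy other than progression or death, among them adverse events, refusal, non-compliance and "Physician determines it is in patient's best interest". Under Section 7.2 these patients are still followed, at 30 days, 6 months and 12 months after the last protocol therapy and then annually.

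**The concern.** Take a patient who stops in Cycle 1 for one of those other reasons. Route 2 fails because a full cycle was not completed. Route 1 fails because any later progression or death happens off protocol therapy. Unless a response is confirmed, route 3 fails too. The patient has been treated and is still being followed, but is absent from the primary response rate, and another patient takes the place.

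Section 10.4 makes the gap more visible. It gives early progression a best response of progressive disease with no on-therapy condition, so 9.4 is narrower than the protocol's own response classification.

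The evaluable denominator feeds both the reported response rate and the two-stage decision in 9.2. With 9 patients in stage 1 and 21 in all, one or two omitted patients can matter. Section 9 plans no response analysis in all treated patients, so a reader of the results would not see how many were left out, or why.

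**Working it through.** **1. Reproduce the stated design (9.2).** Inputs: 9 patients in stage 1, continue with 6 or more responses; 12 more in stage 2, effective with 16 or more of 21; rates of 60% and 85%.

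P(effective | p) = Σ over x = 6 to 9 of C(9,x) p^x (1−p)^(9−x) × P(Bin(12,p) ≥ 16−x)

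- p = 0.60: 0.0905 (stated 9.05%).
- p = 0.85: 0.9040 (stated 90.40%).
- Early termination at 0.60: P(Bin(9,0.60) ≤ 5) = 0.5174 (stated 51.74%).
- Expected size at 0.60: 9 + 12 × (1 − 0.5174) = 14.8 (stated 14.8).

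All four agree.

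**2. Direction.** Let d be the share of treated patients lost through this gap. A confirmed response always qualifies under route 3, so everyone lost lacks one. Then

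evaluable rate = all-treated rate / (1 − d),

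which is never below the all-treated rate.

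**3. Effect on the decision.** Set the all-treated rate at 60% and put the resulting evaluable rate through the same rule. The documents give no value for d, so it is assumed.

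| d (assumed) | Evaluable rate | P(declared effective) |
|---|---|---|
| 0% | 60.0% | 9.05% |
| 2% | 0.60/0.98 = 61.2% | 11.0% |
| 5% | 0.60/0.95 = 63.2% | 14.8% |
| 10% | 0.60/0.90 = 66.7% | 23.7% |

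The last row is an upper bound, because the 10% in 9.1 is a ceiling for inevaluability from all causes.

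**4. Effect at the boundaries.**

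- Success: 16/21 = 76.2%. One patient restored gives 16/22 = 72.7%; two give 16/23 = 69.6%.
- Stage 1: 6/9 = 66.7%. One patient restored gives 6/10 = 60.0%.

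**5. Who falls in the gap.** Sections 4.1.1, 5.2 and 5.3 hold treatment for a dose-limiting toxicity and remove the patient for non-recovery only after 21 days. A hold starting on Day 8 reaches Day 8 + 21 = Day 29, beyond the 28-day cycle. If time on hold counts as time on protocol therapy (an assumption; 9.4 does not say), that patient meets route 2. Non-recovery from toxicity therefore opens the gap only when it starts in about the first week. The other entries are refusal, physician decision, non-compliance and similar stops.

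**6. How open route 3 is to an early stopper.** Section 10.4 requires two consecutive determinations at least 3 weeks apart. The window is 6 × 28 = 168 days. After a Cycle 1 stop, scheduled evaluations come at 30 days and then at 6 months, which is already past Day 168. Only one scheduled scan falls inside the window, so confirmation would usually need unscheduled imaging.

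**7. Likely size.** In the pediatric phase 1 study (2.4.1), 1 of 24 patients (4.2%) discontinued for an adverse event at any time. Adverse-event stops confined to Cycle 1 would be no more frequent than that in the same data. The figure does not cover refusal or physician decision.

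**The case against.** The strongest defense is that this is an ordinary minimum-exposure rule. Section 9.3 openly defines the rate among evaluable patients, and 9.05% is correct for that rate. Many early stoppers will have no scheduled scan, so calling them failures is a convention, not an observation. That stands as a description of the target. It does not explain why a death or documented progression shortly after stopping should go uncounted, nor does it supply the all-treated figure.

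A second defense is that "All other patients will be considered non-responders" already covers these patients. It can be read that way for the two-stage decision. But if it covered inevaluable patients, the evaluable denominator in 9.3 and the replacement in 9.1 would have no purpose. The two readings give different denominators and the text does not choose between them.

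A reader might also go further than the documents allow:

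- **That early stoppers enter mainly as responders, for instance after switching to commercial drug.** Step 6 shows the route is nearly empty, and no section describes a Cycle 1 switch. Commercial supply is mentioned for ineligible patients (3.2.5) and after 26 cycles (2.5, 4.1.3.2).
- **That any toxicity stop in Cycle 1 is lost.** The 21-day hold limits this to toxicity starting in about the first week.
- **That the primary rate as a whole can only be too high.** The direction holds for this gap alone. Other rules lower the rate: an unresected patient with one cycle on therapy and no centrally confirmed response is a non-responder.
- **That the real error rate is 23.7%.** That would need the whole 10% allowance to consist of this one subgroup.

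**Conclusion.** The gap is real in the text. Read literally, 9.4 with 9.1 and 9.3 omits and replaces a treated patient who leaves in Cycle 1 for a reason other than progression or death and has no confirmed response. For these patients the omission can only leave the rate unchanged or raise it relative to all treated patients.

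The size is probably small. At an assumed loss of 2% to 5%, the chance of declaring efficacy when the all-treated rate is 60% is 11.0% to 14.8%, against 9.05%. This rests on three assumptions: the share lost, that those lost are replaced as 9.1 says, and that 60% is meant as the rate among treated patients. The documents do not say how many patients, if any, were affected. The point supports a cheap improvement in reporting and wording. It does not show that the design calculation is wrong or that the trial's conclusion is unsafe.

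**What to change.** In 9.3, add the response rate in all patients who received at least one dose, counting anyone without a centrally confirmed CR or PR within 6 cycles as a non-responder. Report it beside the evaluable rate, with a list of each inevaluable patient and the reason. Reconcile 9.4 with 9.1 and 9.3 so that the text says plainly whether an early stopper without a confirmed response is a non-responder or is replaced.

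Section 2.7.1 says accrual is complete and that larotrectinib was highly active, so the all-treated rate should be added as a supplementary analysis. Changing the decision denominator now would be a change made after results are known. It would also cost power if 85% was meant for evaluable patients: with 5% lost, 0.85 × 0.95 = 80.75%, and the same rule applied to all treated patients has 77.7% power.

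The cost is a few sentences and one extra line in the results, with no new patients or data. The downside is that the all-treated rate may be slightly lower than the evaluable rate.
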